10.4. Interim analysis

There is no planned interim analysis in this investigation.

10.5. Statistical reason for termination of investigation

There will be no interim analysis and therefore no reason to terminate the investigation based on statistical considerations.

10.6. Deviation(s) from statistical design, method, or analytical procedures

Any deviations from the statistical plan will be documented in the clinical investigation report.

11. Data management

11.0. Data collection and data management

Data Collection in the clinical investigation

Data management and the final statistical analyses of all measurements described in this protocol are carried out by [REDACTED] Coloplast A/S.

Data will be collected through an electronic data capturing (EDC) system on electronic Case Report Form (eCRF), a secure, internet-based case report form. This system will be used to record all subject information collected in the investigation for secure data tracking and centralised data monitoring ("remote monitoring") done by monitors, as defined in the monitoring plan.

The EDC system used [REDACTED] The system is designed to be compliant with the FDA requirements of 21 CFR part 11. It is a validated data management system allowing only qualified and trained personnel to enter the system. The system has full audit trail and electronic signature.

The sponsor will be responsible for training the investigator or delegate, in completion of the eCRF.

Principal Investigator, or delegate, at the clinical site will perform primary data collection directly into the eCRF or drawn from source-document (medical records) reviews. The eCRF will be completed on a continuous basis starting from the point of enrolling the subject to final follow up.

The eCRF will be completed by the investigator, or delegate, who have signed the Site Personnel Signature and Delegation List and Clinical Investigation Training Log. It will be the responsibility of the investigator to ensure that all measurements and observations are correctly noted in the eCRF.

All assessments and observations throughout the investigation for each subject must be carefully recorded in an eCRF or in a paper CRF (pCRF) during the visit or immediately after. The eCRF makes it possible to enter data right away when they are obtained. This is the preferred way of collecting data. In case this is not possible the data should be entered no later than 7 days after the visit / procedure.

Adverse events should be registered following the timelines described in the Adverse Event section.

In addition, an electronic patient-reported outcome (ePRO) app that collects subject responses to questionnaires/diaries and transfers data to the [REDACTED] Clinical Cloud will be used in this investigation. The subject will be required to download and install the Patient Cloud app onto their smart phone.

This Patient Cloud app is used during the investigation every time the subject makes a bag (2pc) change.

The ePRO used is [REDACTED] All data will be transferred automatically into the eCRF. If for some reason the app is not available before FPI the patient reported outcome questionnaires will be reported by using a paper diary which will be handed out to all subjects.

In the unforeseen situation, where site cannot establish connection to the EDC system a paper CRF (pCRF) has been printed and supplied by sponsor.

The investigator will keep a separate list of the subjects' ID numbers, names and addresses in a locked room/cabinet. Only data referred to in this clinical investigation plan will be recorded in the CRFs.

Database Management, Queries and Quality Control

The data management system has restricted role-based access control. The principal investigator or delegate must be trained in the system prior to getting access. The training is web-based and must be completed before access to the investigation is granted. Training will be documented in the data management system. Only the principal investigator, or delegate, will be authorised to enter data in the eCRF.

The monitor, using his/her personal login information shall verify all critical data points against the source documents and issue electronic queries for the authorised clinical site personnel to respond, as defined in the monitoring plan.

The principal investigator, using his/her personal login information shall sign each eCRF.

Automated, real time access to the data enable control on study compliance and safety assessments.

A critical quality control will be performed by the sponsor's data management team and queries issued where needed. Such queries will be reviewed by the monitor and must be resolved by the site personnel.

At the end of the study a formal data review meeting will be performed before the database will be locked.

A full audit trail ensures, that each user's (site personnel, monitor, sponsor, data manager) access to and actions in the system is tracked.

The Data Management Procedures are further described in the Data Management SOPs.

11.1. Remote monitoring

Remote (source data verification) and/or centralized (data review) monitoring is carried out by sponsor personnel or representatives (e.g., data management personnel, statisticians, or clinical monitors) at a location other than the site(s) at which the clinical investigation is being conducted (evaluation without visiting the investigation site). Remote monitoring processes can provide many of the capabilities of on-site monitoring as well as additional capabilities.

In addition to onsite monitoring visits, remote monitoring of the data entered in the e-CRF system could be used to achieve the following:

- Conduct activities such as: standard checks of range, consistency, and completeness of data and checks for unusual distribution of data, such as too little variance)
- Special attention will be given in case of frequent data anomalies or errors, protocol deviations or excessive dropouts.
- Augment on-site monitoring by performing monitoring activities that can only be accomplished using centralized processes (e.g., statistical analyses to identify data trends not easily detected by on-site monitoring)

- Monitor data quality through routine review of submitted data in real-time to identify missing data, inconsistent data, data outliers, and potential protocol deviations that may be indicative of systemic and/or significant errors in data collection and reporting at the site
- Verify source data remotely, provided that both source data and CRFs can be accessed remotely
- Conduct aggregate statistical analyses of study data to identify subject data that are outliers relative to others and to evaluate individual subject data for plausibility and completeness
- Conduct analyses of site characteristics, performance metrics (e.g., high screen failure rates, high frequency of eligibility deviations, and delays in reporting data), and clinical data to identify early on corrective actions needed for characteristics correlated with poor performance or noncompliance

11.2. Data retention

All investigation site documents must be archived for a minimum period of 10 years after the final clinical investigation report has been signed. The monitor is responsible for informing the investigator and the CM if this period should be longer for their sites according to local regulation.

12. Amendments to the Clinical Investigation Plan

No changes in the clinical investigation procedures shall be affected without mutual agreement between the principal investigator and the sponsor. The agreement of the changes must be documented by signing the corresponding clinical investigation plan amendments and registered in the Change Log.

All significant changes require notification to the IRB and applicable regulatory authority. Substantial changes may require approval from the IRB and applicable regulatory authority prior to implementation.

13. Deviations from the Clinical Investigation Plan

Deviations to the Clinical Investigation Plan occurs when the activities during the clinical investigation do not comply with the IRB and approved investigation plan.

A minor deviation is defined as those that don't increase risk or decrease benefit or don't have a significant effect on the subject's rights, safety, or welfare; and/or on the integrity of the data. If a deviation increases risk or decreases benefit and/or; has a significant effect on the subject's rights, safety, or welfare and/or has a significant effect on the integrity of the data it is defined as a major deviation and the Investigator must inform the monitor immediately, and the Monitor will report and inform the Clinical Manager or designee immediately.

The investigator is not allowed to deviate from the Clinical Investigation Plan unless, under emergency circumstances or to protect the rights, safety, and welfare of the subject(s).

For the purposes of this investigation, any variance from the protocol is considered a deviation and is to be reported.

The site will complete a deviation eCRF form for all data-related deviations and all deviations that are not related to the data (for example, an untrained nurse performing study procedures) are reported by the monitor in the Site Report – Periodic Monitoring and actions are addressed to the Investigator for completion.

If any deviations to the investigation plan are detected during the monitoring visit, the Monitor shall ensure the site reports all deviations in the eCRF or on the Deviation log in the Investigator File. Additionally, the monitor must report any deviation noted during the visit in the Periodic Monitoring Report.

Monitor will align with data management in each investigation, how data management will be informed about all deviations.

The following information about the deviation will be collected:

- Site ID, Subject ID
- Deviation Date and Investigation Visit

- Date deviation was discovered
- Clear and concise description of the event
- Provide a reason and record the corrective action taken, including the date of the corrective action. Please note corrective action can be site was re-educated on a procedure. Ensure the corrective action is documented.
- Record the IRB notification date, when applicable, and retrieve a copy of the IRB Submission Letter for the TMF.

14. Device Accountability

All access to the investigational devices (including comparators) used in the clinical investigation is controlled by storage procedures and device accountability logs as described below. The investigational devices must only be used in this clinical investigation and only according to the CIP.

Sponsor keeps a device accountability log that states the physical location of all investigational devices from shipment of investigations devices to the investigational sites until return of or disposal.

The PI or an authorized designee keeps records documenting the receipt, use and return and disposal of the investigational devices, which includes:

- Date of receipt.
- Identification of each investigational device (batch no./serial no./lot no.).
- Number of products received
- Number of products distributed to subject
- The expiry date, if applicable.
- The date(s) of use.
- Subject identification.
- The date on which the investigational device was returned/explanted from the subject, if applicable.
- The date of return unused, expired or malfunctioning investigational devices, if applicable.

15. Statement of compliance

The clinical investigation is conducted in accordance with:

- Ethical principles that have their origin in the Declaration of Helsinki, 1964, Last amended at the 59th WMA General Assembly, Brazil, October 2013.
- FDA Regulations
- ISO 14155:2020 "Clinical Investigation of medical devices for human subjects – Good clinical practices".

15.0. Ethics committee and regulatory authorities

The CIP and/or other relevant documents are submitted to the appropriate IRB, if applicable. This clinical investigation will not begin until the required approval from the IRB has been obtained. Any amendment to the clinical investigation plan will be submitted to the same IRB. Sponsor will notify the relevant IRB of the end of the clinical investigation.

15.1. Data protection

As part of the investigation Coloplast A/S, [name] ("Coloplast") will collect and process the personal information the subject provides for the investigation ("subject personal data"). This includes identification and contact information (which may be anonymised depending on the nature of the investigation) as well as information about product usage experience and your health. Coloplast will comply with the EU General Data Protection Regulation (GDPR) and the Danish act on data protection ("databeskyttelsesloven"), including in connection with transfer of data to third countries, cf. chapter V of GDPR, Coloplast will only process the subjects' personal data:

1. To conduct the investigation and carry out related research based on subject consent (primary use), cf. articles 6(1)(a) and 9(2)(a) of GDPR,
2. To comply with applicable legal obligations to e.g. ensure reliability and safety, cf. article 6(1)(c) in conjunction with article 9(1)(i) of GDPR, and
3. If separate consent is given for secondary use of subject personal data, cf. articles 6(1)(a) and 9(2)(a) of GDPR – carry out research outside the clinical protocol to improve Coloplast's products and services, and for use in education.

Part of Coloplast's processing is carried out on third-party platforms (clinical trial databases) and certain third parties are assisting Coloplast in the processing (e.g. the investigator). Such cases will imply a transfer of your personal data to the third parties, but solely for the specified purposes and with the third parties acting on instruction from Coloplast. Data may be collected and processed across the Coloplast network, which may entail processing of personal data outside the European Economic Area. In such cases, an adequate level of protection will be ensured by the third parties being subject to the standard contractual clauses on data protection adopted by the EU or to an EU-approved certification mechanism on data protection. For further information about this please the subject can always consult Coloplast's data protection officer (details below).

Subject personal data will be kept as long as required under applicable laws and regulations. The EU Medical Device Regulation obligates Coloplast to keep the data for a period of at least ten years after the investigation is completed, or, in the event that the device is subsequently placed on the market, at least ten years after the last device has been placed on the market. Subject personal data will be deleted at the end of the mandatory retention period.

If the subject has questions or queries regarding Coloplast's handling of personal information, the subject can always contact Coloplast's Data Protection Officer at [REDACTED] Complaints related to Coloplast's handling of subject personal information may similarly be sent to the Data Protection Officer, and the subject is also entitled to file a complaint with the relevant supervisory authority, which in the case of Denmark is the Danish Data Protection Agency (www.datatilsynet.dk).

The subject can write to [REDACTED] at any time to request:

- Access to personal data
- Correction of errors in personal data or to erase personal data
- Limit what can be done with personal data
- To receive personal data in machine-readable format (data portability).
- Withdrawal of consents the subject has given Coloplast to process personal data

15.2. Indemnity

All subjects are fully covered by Coloplast A/S insurance throughout the investigation.

15.3. Financial conditions

Coloplast A/S will compensate all investigators involved in the clinical investigation for their time and resources spent on the investigation. All financial agreements with the investigation sites involved in the clinical investigation will be specified in a sponsor investigator agreement.

16. Informed consent process

Written informed consent is obtained from all subjects participating in the investigation after thorough written and verbal information. The information is given by the investigator or his/her representative in the subjects' native non-technical language. Each subject will be fully informed about the aim of the investigation, procedures, potential risks, or inconveniences and/or expected benefits and ensure ample time is provided before deciding on participation. The subjects will be informed that their participation is voluntary and that they may leave the investigation at any time, without this having any influence on their further treatment.

The informed consent signature form includes personally dated signatures of the subject and the PI or his/her representative responsible for conducting the informed consent process. A copy will be provided to the subject.

If new information is to be given during the investigation, sponsor will inform the investigators, and the new information is given to the subjects by the investigator. If new information becomes available that can significantly affect a subject's future health and medical care that information will be provided to the subject in written form. CM is responsible for writing the information and providing the approved Subject Information and Consent Form to investigators that will further provide it to the subjects. If applicable, all affected subjects shall be asked to confirm their continuing informed consent in writing.

This procedure also applies to informed consent obtained from a subject's legal representative. The procedure cannot waive the subjects' legal rights.

17. Subject compensation

17.0. Compensation in case of injury

Product liability and No-Fault Clinical Investigation Insurance covering the duration of the clinical investigation are in place, to enable compensation in the event of an injury to a participating subject. .

17.1. Compensation for participating in the clinical investigation

If applicable, subjects will be compensated for their participation in the clinical investigation.

Table 1 Example Compensation for subject participation

Compensation for subject participation	
Initial compensation	£100
Compensation for participation	£100
Compensation for injury	£100
Compensation for death	£100

18. Adverse events, adverse device effects and device deficiencies

18.0. Adverse events

An adverse event is any untoward medical occurrence, unintended disease or injury, or untoward clinical signs (including abnormal laboratory findings) in subjects, whether or not related to the investigational medical device(s) or the comparator(s), or the procedures involved. The adverse event shall be marked with the intensity mild, moderate, or severe. This could include events such as headache or dizziness.

18.1. Adverse device effect

An adverse event, which is related to the use of the investigational medical device, is an adverse device effect, and should be marked as unlikely related, possible related, probable related or with causal relationship on the adverse event form.

The definition of an adverse device effect includes any event resulting from insufficiencies or inadequacies in the instruction for use, or any malfunction of the medical device, as well as any event resulting from use error or from intentional misuse of the device.

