18.2. Device deficiency

A device deficiency is the inadequacy of the investigational medical device or comparator with respect to its identity, quality, durability, reliability, usability, safety, or performance. This includes malfunctions, use errors and inadequacy in the information supplied by the manufacturer including labelling.

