18.7. Medical care of subjects

Principal investigator shall ensure that adequate medical care is provided, during and after participation in the clinical investigation, to a subject experiencing an adverse event. All ongoing ADEs, SAEs, SADEs and DDs that could have led to a SAE at subject termination will be followed until resolution. An ongoing adverse event at subject termination visit is documented as the current status for the adverse event and will not be followed up.

The subjects shall be informed of any new significant findings occurring during the clinical investigation, including the need for additional medical care that can be required, and of the nature and possible cause of any adverse events experienced.

Principal investigator shall provide the subject with the necessary instructions on proper use, handling, storage and return of the investigational device and comparator when it is used or operated by the subject.

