18.8. Reporting and timelines

18.9. Investigator's reporting responsibilities

PI at each site must assess all (S)AE's that occur at his/her site.

- All serious adverse events and serious adverse device effects must be reported to sponsor within 24 hours of the site becoming aware of the event.

- A device deficiency that could have led to a serious adverse event but did not because suitable action was taken, intervention had been made or because of fortunate circumstances should be reported to sponsor within 24 hours of the site becoming aware of the event.
- New findings and/or updates in relation to already reported serious events should also be reported to sponsor within 24 hours of the site becoming aware of the event.
- Device deficiencies and all adverse device effects related to CE marked Coloplast investigational product and/or comparator must be reported to sponsor within 24 hours of becoming aware of the event.

When reporting the SAE, the relationship to the test material shall be described whether the event is considered

- **Not related**, the event has no temporal relationship with the use of the test material or the procedures.
- **Unlikely related**, the relationship with the use of the test material seems not relevant and/or the event can be reasonably explained by another cause, but additional information may be obtained.
- **Possible related**, the relationship with the use of the test material is weak but cannot be ruled out completely. Alternative causes are also possible (e.g. an underlying or concurrent illness/ clinical condition or/and an effect of another device, drug, or treatment). Cases where relatedness cannot be assessed, or no information has been obtained should also be classified as possible.
- **Probable related**, the relationship with the use of the test material seems relevant and/or the event cannot reasonably be explained by another cause, but additional information may be obtained.
- **Definitely related/Causal relationship**, the event has a temporal relationship with the test material use/application or procedures.

The investigator will assess intensity for each AE and SAE reported during the investigation and assign it to one of the following categories:

- **Mild**, the intensity of the event is mild with no further action or intervention
- **Moderate**, the intensity of the event will lead to an action or intervention to solve the event

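### Sections 18.1 and 18.9 conflict with the rest of the plan on whether a comparator-related event counts as an adverse device effect

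*Combined protocol and SAP*

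**What the plan says.** Section 18.0 defines an adverse event as covered "whether or not related to the investigational medical device(s) or the comparator(s), or the procedures involved". Section 18.2 does the same for deficiencies: "A device deficiency is the inadequacy of the investigational medical device or comparator". Section 18.1, between the two, names one product only: "An adverse event, which is related to the use of the investigational medical device, is an adverse device effect". Section 18.4 defines the serious adverse device effect (SADE) as an ADE with serious consequences, so it takes its scope from 18.1.

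Section 18.9 then says two things. On causality: "When reporting the SAE, the relationship to the test material shall be described", followed by a five-step scale that refers throughout to that material. On reporting: "Device deficiencies and all adverse device effects related to CE marked Coloplast investigational product and/or comparator must be reported to sponsor within 24 hours".

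The ADE label has consequences. Sections 7.2 and 18.7 follow ongoing ADEs until they resolve. For adverse events outside the listed classes, 18.7 says: "An ongoing adverse event at subject termination visit is documented as the current status for the adverse event and will not be followed up". Section 18.11 gives the Medical Advisor lists of AEs and ADEs related to the investigation product or the clinical investigation, and does not name the comparator.

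**The concern.** In a crossover trial every subject is meant to wear both products, so a safety class that may cover only one of them is a problem. If 18.1 is applied as written, the same non-serious skin reaction is an ADE when attributed to the new coupling and a plain adverse event when attributed to SenSura Mio Click. The label decides whether an event still ongoing at the end is followed, and it may decide whether the Medical Advisor sees it. It would also distort any tabulation of ADEs or SADEs by product: comparator events would be under-counted, to the apparent disadvantage of the test product.

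**Working it through.** No arithmetic applies. The check sets the uses of the terms side by side and then traces one event through the rules.

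**Where the comparator stands in each section**

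| Section | Term used | Comparator covered? |
|---|---|---|
| 18.0 | investigational device(s), comparator(s) | Yes, named separately |
| 18.1 | investigational medical device | Not named |
| 18.2 | investigational device, comparator | Yes, named separately |
| 18.4 | ADE | Inherits 18.1 |
| 18.7 | investigational device and comparator (instructions to subjects) | Yes, named separately |
| 18.9, causality | test material | Term not defined |
| 18.9, ADE reporting | CE-marked investigational product and/or comparator | Yes, named separately |
| 18.11 | investigation product | Not named |
| 4.3 | investigational products | Yes, by an explicit parenthesis |
| 14 | investigational devices | Yes, by an explicit parenthesis |
| 5.8 | comparator investigational product | Yes, as a kind of investigational product |
| 7.1, Visits 2 and 3 | investigational product: test or comparator | Yes |

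The plan thus uses two meanings. Most of section 18 treats the device and the comparator as different things. Sections 4.3, 5.8, 7.1 and 14 put the comparator inside the broader term. Section 18.1 carries neither the separate mention nor the parenthesis, so it can be read either way.

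**One event traced under both readings**

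Take a non-serious reaction that the investigator attributes to the comparator and that is still ongoing at Visit 4.

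1. *18.1 read alone.* It is an adverse event and not an ADE. Under 18.7 its status is recorded and it is not followed. Under 18.11 it may or may not be listed. The ADE reporting rule in 18.9 has nothing to act on, although it names the comparator.
2. *18.1 read together with the reporting rule in 18.9 and with sections 4.3 and 14.* It is an ADE. It is followed to resolution under 7.2 and 18.7, and it falls under the reporting rule in 18.9 if the product is CE marked.
3. *The same reaction attributed to the test product.* It is an ADE under both readings.

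Now make the comparator event serious. Under both readings it goes to the sponsor within 24 hours (18.9) and to the authorities within the stated limit (18.10). It is followed to resolution as an SAE (18.7), and it is provided to the Medical Advisor under the opening sentence of 18.11. Only the SADE label changes.

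The difference in handling is therefore confined to non-serious events. The difference in classification covers both ADEs and SADEs.

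**The case against.** The strongest reply is that section 18 already answers the question. Section 18.9 requires reporting of "all adverse device effects related to CE marked Coloplast investigational product and/or comparator", which makes sense only if comparator ADEs exist. Section 14 uses nearly the same noun as 18.1 and includes comparators, and the visit procedures in 7.1 use the broad meaning. *Test material* differs from *test product*, the plan's name for the new coupling, and 7.1 speaks of testing both products.

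This stands in part. It defeats several stronger readings that a reader might infer:

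- **That comparator events cannot be ADEs, so that the comparator rate is zero by construction.** This follows from 18.1 alone. Section 18.9 contradicts it.
- **That SAE causality is graded only against the new coupling.** The text supports no more than that the term is undefined.
- **That the trial's safety comparison is biased.** The safety assessments in 5.5 are adverse events and device deficiencies, and both definitions cover the comparator. No between-product comparison of ADEs is planned, and the aim of being on par concerns leakage at the coupling.
- **That everyone finishing on the comparator is affected: 50/2 = 25 randomised, or 40/2 = 20 completers.** That is a count of people and not of events. Relatedness attaches to the product that caused the event, not the one worn last, and a period 1 event may still be ongoing at Visit 4.

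What the reply does not do is remove the conflict. The reporting rule in 18.9 shows that comparator ADEs are expected, but it does not supply the definition that 18.1 leaves out. Because it lists investigational product and comparator as separate terms, it also lends weight to the narrow reading of 18.1.

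**Conclusion.** The inconsistency is real and worth correcting before the plan is used. Its reach is limited: the classification of comparator-related events as ADEs or SADEs, the follow-up of non-serious ones ongoing at the end, and possibly their listing to the Medical Advisor. That any comparator event would be handled differently is a risk under the literal reading of 18.1 and not a stated rule.

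The number of affected events cannot be estimated, because the documents give no adverse event rate for either product. The conclusion assumes that whoever classifies events may apply 18.1 as it stands. Three things are unknown from the documents: the layout of the adverse event form, the CE-mark status of the test product (which decides whether the 24-hour ADE rule reaches it), and whatever follows the start of the intensity scale in 18.9, which is not in the available text. Nothing is inferred from these.

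**What to change.** Reconcile the passages so that one definition covers both products:

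- In 18.1, add *or the comparator* after the investigational medical device, as 18.0 and 18.2 already do. Section 18.4 then follows without further change.
- In 18.9, replace *test material*, or define it as the test or comparator product.
- In 18.11, use the same term, so that the Medical Advisor's lists have the same scope for both products.
- Make sure that relatedness is recorded by product. If the adverse event form already does this, nothing needs adding.

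The cost is a few words in three sections and at most one field on a form, with no extra subjects or visits. The downside is that a few comparator events may be newly classed as ADEs and receive the follow-up already planned for that class.
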